3.0 Data management

Study participants will be assigned a unique code to enable data linkage throughout follow-up. All data will be entered into an electronic management system by research team member. To ensure accurate data

entry, we will check data entry for a random 10% sample records entered after that. Data collection and study conduct will be monitored through weekly meeting with the research team.

4.0 Discussion

This study will explore a novel approach of bridging TCM and WM, i.e., investigating the utility of an established WM therapy for mitigating a condition defined by TCM principle. Specifically, this study will investigate the potential using β -glucan to improve PQi and GQi in participants with PQD. Given the lack of stringent criteria of PQD diagnosis, this study will seek the proof-of-principle of standardized diagnostic PQS and GQS developed by experts' panel, especially on PQS.

15. RStudio Team (2020). RStudio: Integrated Development Environment for R. RStudio, PBC, Boston, MA URL <http://www.rstudio.com/>.

Table 1. Calculation of Standardized Protective Qi Score (PQS)

Category	Parameter	Weight
Cold History	TCM Inquiry (Cold frequency)	25%
Symptoms of PQD	TCM Inquiry (Spontaneous sweating)	16.7%
	TCM Inquiry (Aversion to wind & cold)	16.7%
Sign of PQD	TCM Inspection (Tongue)	8.3%
	TCM Auscultation (Low voice & apathy)	6.7%
	TCM Palpation (Overall Pulse)	10%
	TCM Palpation (Cun Pulse)	16.7%

The PQS were obtained from the standardized protocol shown in Table 2, and the weighting coefficients were based on TCM investigators' clinical experience.

Table2: Standardized criteria for PQS assessment

Candidate Parameter		Method of measurement and scores	
Cold Frequency	TCM Inquiry (Cold frequency)	No cold in the past 2 months	0
		Once in the past 2 months	1
		Twice in the past 2 months	2
		3 times or more in the past 2 months	3
Symptoms of PQD	TCM Inquiry (Spontaneous sweating)	No spontaneous sweating, sweat only with intense physical activities	0
		Sweat with routine physical activities	1
		Sweat heavily with routine physical activities	2
		Sweat with slight physical activities like walking	3
		Sweat spontaneously	4
	TCM Inquiry (Aversion to wind & cold)	No aversion to wind or cold	0
		Aversion to wind	1
		Aversion to cold, but relieved by adding light clothing	2
		Aversion to both cold (but relieved by light clothing) and wind, or susceptible to cold when exposed to wind or cold	3
		Aversion to cold (only relieved by thick clothing that covers whole body); or very easily catch a cold when exposed to wind or cold	4
Sign of PQD	TCM Auscultation (Low voice & apathy)	The participant's voice is loud & clear at a distance of 2m from the investigator	0
		The participant can be heard & understood at 2m from the investigator, but the voice is recognizably weak.	1
		The participant's voice is clearly low at 2m from the investigator & needs much attention to understand.	2
		The participant can be heard from 2m but need repeated clarification.	3
		The participant cannot be heard with a clear understanding at a distance of 2m.	4
	TCM Inspection (Tongue)	The tongue looks light red with thin white coating and is of proper size.	0
		The tongue looks pale in color with white coating; however, the tongue is of proper size & has no tooth mark on the sides.	1
		The tongue looks pale with white coating. This size is slightly larger than normal. Tooth-marks are visible but are limited to part(s) of the tip and sides of the tongue.	2
		The tongue looks pale with white coating. This size is significantly larger than normal. Tooth-marks are visible along the full length of the tip and sides of the tongue.	3
	TCM Palpation (Overall Pulse ¹)	Normal pulse	0
		Deficient Pulse is detectable but not apparent	1
		Apparent Deficient Pulse	2
	TCM Palpation (Cun Puls ¹)	Normal pulse	0
		The pulse shows characteristics of Floating or Deficient Pulse, but not both.	1
		Floating pulse is present, Deficient Pulse is detectable but not apparent.	2
		Floating pulse is present, Deficient Pulse is apparent.	3

¹. Overall pulse indicates the overall impression of pulse at the three locations: Cun, Guan, & Chi.

Table 3. Calculation of Standardized Generic Qi Score (GQS)

Category	Parameter	Weight
Cold History	TCM Inquiry (Cold frequency)	20%
Symptoms of PQD	TCM Inquiry (Spontaneous sweating)	10%
	TCM Inquiry (Aversion to wind & cold)	10%
Symptoms of Lung Qi Deficiency	TCM Inquiry (Shortness of breath)	10%
	TCM Inquiry (Unwillingness to talk)	10%
Symptoms of Spleen and Heart Qi Deficiency	TCM Inquiry (Limb weakness)	6.67%
	TCM Inquiry (Lack of energy)	6.67%
	TCM Inquiry (Low spirit, fatigue)	6.67%
Signs of GQD	TCM Inspection (Tongue)	5%
	TCM Auscultation (Low voice & apathy)	5%
	TCM Palpation (Overall Pulse¹)	5%
	TCM Palpation (Cun Pulse)	5%

The GQS were obtained from the standardized protocol shown in Table 4, and the weighting coefficients were based on TCM investigators' clinical experience.

Table 4: Standardized Criteria for Generic Qi diagnosis

Candidate Parameter		Method of measurement and scores	
Cold Frequency	TCM Inquiry (Cold frequency)	No cold in the past 2 months	0
		Once in the past 2 months	1
		Twice in the past 2 months	2
		3 times or more in the past 2 months	3
Symptoms of PQD	TCM Inquiry (Spontaneous sweating)	No spontaneous sweating, sweat only with intense physical activities	0
		Sweat with routine physical activities	1
		Sweat heavily with routine physical activities	2
		Sweat with slight physical activities like walking	3
		Sweat spontaneously	4
	TCM Inquiry (Aversion to wind & cold)	No aversion to wind or cold	0
		Aversion to wind	1
		Aversion to cold, but relieved by adding light clothing	2
		Aversion to both cold (but relieved by light clothing) and wind, or susceptible to cold when exposed to wind or cold	3
		Aversion to cold (only relieved by thick clothing that covers whole body); or very easily catch a cold when exposed to wind or cold	4
Symptoms of Lung Qi Deficiency	TCM Inquiry (Shortness of Breath)	1-10 scale, with 1 indicating the most symptomatic	
	TCM Inquiry (Unwilling to talk)		
Symptoms of Spleen and Heart Qi Deficiency	TCM Inquiry (Limb weakness)	1-10 scale, with 1 indicating the most symptomatic	
	TCM Inquiry (Lack of energy)		
	TCM Inquiry (Low spirit, fatigue)		
Sign of GQD	TCM Auscultation (Low voice & apathy)	The participant's voice is loud & clear at a distance of 2m from the investigator	0
		The participant can be heard & understood at 2m from the investigator, but the voice is recognizably weak.	1
		The participant's voice is clearly low at 2m from the investigator & needs much attention to understand.	2
		The participant can be heard from 2m but need repeated clarification.	3
		The participant cannot be heard with a clear understanding at a distance of 2m.	4
	TCM Inspection (Tongue)	The tongue looks light red with thin white coating and is of proper size.	0
		The tongue looks pale in color with white coating; however, the tongue is of proper size & has no tooth mark on the sides.	1
		The tongue looks pale with white coating. This size is slightly larger than normal. Tooth-marks are visible but are limited to part(s) of the tip and sides of the tongue.	2
		The tongue looks pale with white coating. This size is significantly larger than normal. Tooth-marks are visible along the full length of the tip and sides of the tongue.	3
	TCM Palpation (Overall Pulse ¹)	Normal pulse	0
		Deficient Pulse is detectable but not apparent	1
		Apparent Deficient Pulse	2
	TCM Palpation (Cun Puls ¹)	Normal pulse	0
		The pulse shows characteristics of Floating or Deficient Pulse, but not both.	1
		Floating pulse is present, Deficient Pulse is detectable but not apparent.	2
	Floating pulse is present, Deficient Pulse is apparent.	3	

¹. Overall pulse indicates the overall impression of pulse at the three locations: Cun, Guan, & Chi.

Appendix I

Participant questionnaire (Qi-related information)

Part I

Do you have a history of **catching** a cold* (*, defined by TCM) in the past year? If no, please proceed to Part II of this section; if yes, please fill out the following blanks.

1. How many times did you **catch** a cold* in the **past year**?
 - i. Once duration:

 - ii. Twice duration of cold #1:
duration of cold #2:

 - iii. 3 times or more duration of cold #1:
duration of cold #2:
duration of cold #3:
duration of other colds:

 - iv. During the above colds*, did you experience any of the following symptoms:
 - Sneezing
 - Coughing
 - Sweating
 - Nasal discharge or congestion
 - Itching or painful throat
 - Headache
 - Aversion to wind and cold
 - General pain and malaise
 - High fever (body temperature > 39.1⁰C)

2. How many times did you **catch** a cold* **last winter (2017 – 2018)**?
 - i. Once duration:

 - ii. Twice duration of cold #1:

duration of cold #2:

iii. 3 times or more

duration of cold #1:

duration of cold #2:

duration of cold #3:

duration of other colds:

iv. During the above colds*, did you experience any of the following symptoms:

- Sneezing
- Coughing
- Sweating
- Nasal discharge or congestion
- Itching or painful throat
- Headache
- Aversion to wind and cold
- General pain and malaise
- High fever (body temperature > 39.1⁰C)

3. How many times did you **catch** a cold* in the **last two months**?

i. Once

duration:

ii. Twice

duration of cold #1:

duration of cold #2:

iii. 3 times or more

duration of cold #1:

duration of cold #2:

duration of cold#3:

duration of other colds:

iv. During the above colds*, did you experience any of the following symptoms:

- Sneezing
- Coughing

- Sweating
- Nasal discharge or congestion
- Itching or painful throat
- Headache
- Aversion to wind and cold
- General pain and malaise
- High fever (body temperature $> 39.1^{\circ}\text{C}$)

4. How many days have elapsed since you last experienced symptoms of a cold*? If you currently have an ongoing cold, write “ongoing”.

Part II

1. Do you have spontaneous perspiration?
 - a. I don't readily sweat, or sweat only with intense physical activities
 - b. I sweat with some slight physical activities like walking
 - c. I sweat spontaneously
 - d. I sweat heavily and instantly with physical activities
 - e. I sweat even without any physical activities

2. Aversion to wind or cold
 - a. No aversion to wind or cold
 - b. Aversion to wind
 - c. Aversion to cold, but relieved by adding clothing
 - d. Aversion to both cold (but relieved by clothing) and wind, or susceptible to cold* when exposed to wind or cold weather
 - e. Aversion to cold (only relieved by clothing that covers whole body), very readily catch a cold* when exposed to wind or cold weather

Part III

1. Do you often feel shortness of breath?
2. Do you often feel unwillingness to talk?

Part IV

1. Do you often feel limb weakness?
2. Do you often feel a lack of energy?
3. Do you often feel in low spirits?

Part V

1. Do you often have cough?
2. Do you often have thin sputum
3. Do you often feel timidity
4. Do you have nasal allergies (stuffy and itchy nose, runny nose with clear drainage)?

Part VI

1. Do you often have poor appetite?
2. Do you have loose stools
3. Do you often have uncomfortable feeling in the abdomen after eating?

Part VII

1. Do you often feel palpitations?
2. Do you often feel depressed?

Part VIII

1. Do you have frequency of urination?
2. Do you often feel soreness of lower back?
3. Do you have cold limbs, especially legs?

Appendix II

Physical Examination

Part I

1. Height:
2. Weight:
3. Blood Pressure:
4. Heart Rate:
5. Respiration Rate:

Part II

1. weak or powerless pulse
2. cun-pulse superficial or weak
3. corpulent tongue or with white fur
4. low voice

Appendix III

Participant questionnaire – Section II (Generic Qi-related information)

Part I

1. Did you catch any cold* (*as defined by TCM) in the past two weeks?
 - a. If no, please proceed to Part II
 - b. If yes: how many times, and how long did it last?
 - v. Once duration:
 - vi. Twice duration of cold #1:
duration of cold #2:
 - c. During the above colds*, did you experience any of the following symptoms:
 - Sneezing
 - Coughing
 - Sweating
 - Nasal discharge or congestion
 - Itching or painful throat
 - Headache
 - Aversion to wind and cold
 - General pain and malaise
 - High fever (body temperature $>39.1^{\circ}\text{C}$)
 - d. How many days have elapsed since you last experienced symptoms of a cold*? If you currently have an ongoing cold, write “ongoing”.

Part II

3. Do you have spontaneous perspiration?
 - a. I don't readily sweat, or sweat only with intense physical activities
 - b. I sweat with some slight physical activities like walking
 - c. I sweat spontaneously
 - d. I sweat heavily and instantly with physical activities
 - e. I sweat even without any physical activities
4. Aversion to wind or cold
 - a. No aversion to wind or cold

- b. Aversion to wind
- c. Aversion to cold, but relieved by adding clothing
- d. Aversion to both cold (but relieved by clothing) and wind, or susceptible to cold* when exposed to wind or cold weather
- e. Aversion to cold (only relieved by clothing that covers whole body), very readily catch a cold* when exposed to wind or cold weather

Part III

- 1. Do you often feel shortness of breath?
- 2. Do you often feel unwillingness to talk?

Part IV

- 1. Do you often feel limb weakness?
- 2. Do you often feel a lack of energy?
- 3. Do you often feel in low spirits?

Part V

- 1. Do you often have a cough?
- 2. Do you often have thin sputum
- 3. Do you often feel timidity

Part VI

- 1. Do you often have poor appetite?
- 2. Do you have loose stools
- 3. Do you often have uncomfortable feeling in the abdomen after eating?

Part VII

- 1. Do you often feel palpitations?
- 2. Do you often feel depressed?

Part VIII

- 1. Do you have frequency of urination?
- 2. Do you often feel soreness of lower back?
- 3. Do you have cold limbs, especially legs?

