2.4 Intervention

After the subjects are consented, a TCM practitioner will evaluate patients in a clinical setting with the objective of identifying subjects with PQD based upon the traditional, qualitative measures of TCM. Simultaneously, we will administer the Subject Record at Screening/1st visit and quantitate the participants' PQD status by employing the Standardized Diagnostic Questionnaire (Appendix I) of PQD. Subjects diagnosed as having PQD based on conventional method will be asked to return to the clinic for a second visit in which a basic physical exam (Appendix II), include that of the head, ears, eyes, nose, throat, etc., will be conducted by the PI to ensure the general health condition of subjects are compliant with the inclusion/exclusion criteria. The qualified subjects will then be re-evaluated for PQD and treated with the dietary supplement Proglucamune for 8 weeks.

Following screening, participants with PQD will begin treatment immediately. All participants will be provided with a bottle containing 60 treatment tablets in a sealed bottle and instructed to consume 2 tablets/day for the next 4 weeks. More specifically, subjects will be asked to consume 2 tablets/day of Proglucamune, a supplement currently marketed by USANA Health Sciences as a supplement that supports robust immune function. If any subjects are taking medications, they will be instructed to take the product at least 3 hours before or after the medication. Written instructions concerning how to consume the treatment, as well as information regarding treatment storage conditions and the contact information of the investigators, will be included with the dietary supplement.

Following treatment, participants will return to the clinic every 2 weeks for a period of 8 weeks for a follow-up assessment of their Protective Qi status (Figure 1). At each clinic visit, subjects will be required to undergo a TCM diagnostic work-up to assess their Protective Qi status and to complete the Subject Record at Follow-up (Appendix III). On day 28 (interim clinic visit #3), participants will return any unused treatment tablets that were provided during the first clinic visit. In addition, they will be provided with an additional allotment of 60 treatment tablets in a sealed bottle, and again instructed to consume 2 tablets/day of Proglucamune for the next 4 weeks. This will provide enough tablets for each subject to complete the study.

[figure not shown]

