2.5.1.1 Change of Protective Qi Score (PQS) assessed by standardized method

Protective Qi of each participant at baseline and each follow-up visit will be measured by an on-site investigator (licensed TCM practitioners) through a standardized quantitative assessment (Table 2). The evaluation includes 3 health conditions relevant to PQD (cold frequency, symptoms, and signs). Each condition will be scored on a 1-10 scale based on a set of standardized criteria (Table 1). The sub-scores will be weighted to arrive at a final PQS. So this PQS will be on a 1-10 scale, with 10 being the most healthy state. The change of the PQS from baseline, indicating the treatment effect, will be calculated and analyzed by statistical means.

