2.5.2.1 Change of Generic Qi Score (GQS) assessed by standardized method

Generic Qi of each participant at baseline and each follow-up visit will be measured by an on-site investigator (licensed TCM practitioners) through a standardized quantitative assessment (Table 4). The evaluation includes 5 sets of criteria indicative of Generic Qi insufficiency (cold history, symptoms of PQD, symptoms of Lung Qi Deficiency, symptoms of Heart and Spleen Deficiency, and signs of GQD). Each set will be scored on a 1-10 scales, with 10 being the most healthy state (Table 3). The sub-scores will be averaged to arrive at a final GQS. So this GQS will be on a 1-10 scale, with 10 being the most healthy state. The change of the GQS from baseline, indicating the treatment effect, will be calculated and analyzed by statistical means.

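### The heaviest item in both Qi scores counts colds over 2 months, but the only follow-up form in the documents asks about two weeks, and nothing says how the item is scored after baseline

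*Combined protocol and SAP*

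**What the plan says.** Table 1 gives cold frequency 25% of the PQS and Table 3 gives it 20% of the GQS. The next largest weights are 16.7% and 10%. Tables 2 and 4 grade the item 0 to 3, from "No cold in the past 2 months" up to three or more colds in that period.

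Section 2.5.1.1 has Protective Qi "at baseline and each follow-up visit will be measured by an on-site investigator (licensed TCM practitioners) through a standardized quantitative assessment (Table 2"). Section 2.5.2.1 does the same for Generic Qi "through a standardized quantitative assessment (Table 4"). In both, change from baseline is taken as the treatment effect.

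The baseline form matches the tables. Appendix I, Part I, question 3 asks "How many times did you catch a cold* in the last two months". The follow-up form does not: Appendix III, Part I, question 1 asks "Did you catch any cold* (*as defined by TCM) in the past two weeks" and offers only once or twice as counts. Section 2.4 requires subjects at each visit to "undergo a TCM diagnostic work-up to assess their Protective Qi status and to complete the Subject Record at Follow-up (Appendix III").

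Sections 2.4 to 2.6, the table notes and the appendices do not say whether two-week answers are summed, added to earlier colds, rescaled or left unused.

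**The concern.** The form planned for follow-up cannot supply the heaviest item as the tables define it. A reader of the results could not tell which window lay behind that item at days 14, 28, 42 and 56.

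The two candidate sources err in different ways. A 2-month recall is true to the tables, but at the early visits it looks back mostly over time before treatment, so it hides early change. A two-week count set against a 2-month baseline count looks like improvement even when nothing has changed, because a shorter window catches fewer colds. PQS change is a primary measure, and the design in section 2.1 is one-group pretest-posttest, so no comparison arm would remove that artefact.

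**Working it through.** **Inputs from the documents.** Weights are 25% (Table 1) and 20% (Table 3). Item levels are 0-3 over 2 months (Tables 2 and 4). The follow-up question covers 14 days with a highest count of 2 (Appendix III). Visits are every 14 days to Day 56 (section 2.4). Exclusion criterion 12 bars cold symptoms in the 7 days before entry.

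**Assumptions, not in the documents.** Two months is 61 days. Colds follow a Poisson process at a constant rate. Levels 0-3 map linearly onto 10-1, so one level is 9/3 = 3 sub-score points. One level is then worth 0.25 × 3 = 0.75 PQS points and 0.20 × 3 = 0.60 GQS points.

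**Step 1: literal 2-month recall.** The pre-treatment share of the window at day t is (61 − t)/61: 47/61 = 77%, 33/61 = 54%, 19/61 = 31% and 5/61 = 8%.

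Suppose treatment truly halves the rate, starting from 1 cold per 61 days.
- The mean item level E[min(N,3)] is 0.977 at the full rate and 0.498 at half the rate. The full effect is 0.75 × (0.977 − 0.498) = 0.36 PQS points.
- At day 14 the expected count is (47 + 0.5 × 14)/61 = 0.885, which gives a mean level of 0.870. The visible effect is 0.75 × (0.977 − 0.870) = 0.08, about 22% of the full effect.
- At days 28, 42 and 56 the visible effect is 0.16, 0.25 and 0.33 points.
- For rates of 0.5-2 per 61 days, the visible share is 20-23%, 42-46%, 66-69% and 91-92% at the four visits.

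**Step 2: two-week answer scored directly, no true change.** Shift = 0.75 × (E[min(N,3)] over 61 days − E[min(N,2)] over 14 days). GQS uses 0.60.

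| Colds a year | Per 61 days | Mean level, 61 days | Mean level, 14 days | PQS shift | GQS shift |
|---|---|---|---|---|---|
| 1 | 0.167 | 0.167 | 0.038 | 0.10 | 0.08 |
| 2 | 0.334 | 0.334 | 0.077 | 0.19 | 0.15 |
| 3 | 0.5 | 0.498 | 0.115 | 0.29 | 0.23 |
| 6 | 1 | 0.977 | 0.228 | 0.56 | 0.45 |
| 12 | 2 | 1.782 | 0.446 | 1.00 | 0.80 |

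**Step 3: allow for exclusion criterion 12.** Being symptom-free before entry shortens the baseline window in which a cold could have started. I took 7 days off, or 7 days plus a cold of 5 or 10 days (assumed), leaving 54, 49 or 44 days. The PQS shift becomes 0.06-0.16 at 1-2 colds a year and 0.18-0.88 at 3-12.

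**Step 4: sources available at Day 56, no true change, 3-12 colds a year.**
- Sum of the four Appendix III counts, capped at 3: PQS shift +0.03 to +0.10 without exclusion 12, −0.01 to −0.22 with it.
- 2-month recall with exclusion 12: −0.01 to −0.23.
- Counting one missed form as zero colds would add 0.09-0.27 PQS points.

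**The case against.** The strongest reply is that the tables settle the matter. Every cold category in Tables 2 and 4 is worded over 2 months, the item is labelled a TCM inquiry, and the practitioner applies those tables at each visit. Section 2.4 lists the diagnostic work-up and the Appendix III form as separate tasks. The form also cannot be the whole score sheet. It has no tongue, voice or pulse item (8.3 + 6.7 + 10 + 16.7 = 41.7% of the PQS weight), its sweating options do not match Table 2, and it asks yes/no-style questions where Table 4 needs a 1-10 rating. It is headed Section II, so another sheet may exist.

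Most of this stands, and it makes the 2-month recall the better reading. It does not close the gap. No follow-up form in the documents has a place for a 2-month count, and at baseline section 2.4 says PQD status is quantitated with the Appendix I questionnaire, which makes scoring from the follow-up form a natural analogy.

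Two further points hold in full. Dilution belongs to the recall window, not to the lack of a control arm: a 2-month recall at day 14 is 77% pre-treatment in any arm, so a controlled trial would be diluted too. The sizes in Step 2 depend heavily on the assumed cold rate; the 1.00-point end needs 12 colds a year.

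**Conclusion.** The mismatch is certain from the text; its size is not. The documents define the item over 2 months, collect two weeks on the only follow-up form they contain, and do not link the two. Under the literal reading, early change on the item is diluted, and by Day 56 only about 8% of the window is pre-treatment. Under direct scoring, the PQS would rise spuriously by the amounts in Steps 2 and 3. Those amounts rest on a constant Poisson rate and a linear mapping. The documents give no cold rate, no conversion to the 1-10 scale, and no SD or expected effect for the PQS against which to judge them.

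A reader might infer that the plan scores the two-week answer, or that the scores were in fact computed wrongly. The documents support neither: direct scoring departs from Table 2, and this is a gap in the scoring rules, not evidence of mis-scoring. Nor does it reach every primary measure, since the conventional PQD status in section 2.5.1.2 is not calculated from this score. The point should be clarified before the PQS and GQS results are interpreted.

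**What to change.** - State that a two-week answer is never scored on the 2-month item.
- At Day 56, score the item from a 2-month recall if one was recorded. Otherwise use the sum of the four Appendix III counts, capped at 3. Count a cold that continues across visits once, and never count a missing form as zero.
- Report the Day 56 change in PQS and GQS with and without the cold item. For the version without it, rescale the remaining weights to 100% and use the same reduced score at baseline.
- At days 14, 28 and 42, show the score without the cold item beside any full score, and state the pre-treatment share of the recall window.

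The cost is a little more analysis; no form changes or new data are needed. There are four downsides. The summed count covers 56 days, not about 61. Exclusion criterion 12 lowers the baseline count, so Day 56 leans slightly against the product (Step 4). The reduced score drops one of the three conditions named for the PQS; because this version is dated June 2021 and section 2.3 puts enrolment in March-April 2018, it should be labelled as added after enrolment. Participants with a missing form or early withdrawal will lack a summed count, so the plan should say how they enter the full-score analysis under the LOCF rule in section 2.6.

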2.6 Statistical analysis

We will follow intention-to-treat method to analyze participants' PQi and GQi change. In the case of missing data that resulted from withdrawn participants or missing visits, the PQi and GQi records from the previous visit will be used (Last Observation Carried Forward, or LOCF, imputation).

Baseline data will be imported into RStudio [15] analysis and reported using descriptive statistics.

Changes in the PQS and GQS at follow-up will be assessed using One-Way ANOVA. Change in the PQi status and GQi status will be assessed using repeated measures logistic regression.

All statistics will be conducted using RStudio.

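### After a missed visit the follow-up form has no field for a cold that began in the skipped two weeks, and no rule says whether the 2-month cold item is scored from that form

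*Combined protocol and SAP*

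**What the plan says.** Section 2.4 sets the schedule: "participants will return to the clinic every 2 weeks for a period of 8 weeks for a follow-up assessment". With Figure 1 this gives Days 14, 28, 42 and 56. Appendix III is completed at each of these visits, and no variant is provided for use after an absence.

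Appendix III, Part I, question 1 reads: "Did you catch any cold* (*as defined by TCM) in the past two weeks". For a negative answer the instruction is: "If no, please proceed to Part II". That passes over item 1d, "How many days have elapsed since you last experienced symptoms of a cold", the only question on the form that could reach back beyond two weeks.

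The score uses a different window. The best level of the cold item in Table 2 is "No cold in the past 2 months", and the levels run from 0 to 3 (three or more colds). Section 2.5.1.1 has the on-site practitioner apply Table 2 at baseline and at every follow-up. Appendix I, the screening questionnaire, contains a matching two-month question (Part I, question 3). Appendix III does not.

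For gaps, section 2.6 says that with "missing data that resulted from withdrawn participants or missing visits, the PQi and GQi records from the previous visit will be used", that is, LOCF.

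**The concern.** The look-back on the form is tied to the day of completion and not to the last attended visit. While every visit is attended the windows join up. Once a visit is missed, the interval before it falls outside every completed follow-up form.

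Illness is a plausible reason for missing a visit, so the uncovered days may be the ones that contain a cold. Cold frequency has the largest single weight in both scores: 25% of the PQS (Table 1) and 20% of the GQS (Table 3). Baseline is asked over an unbroken two months. A cold lost only at follow-up therefore moves the change from baseline towards improvement, and in a one-group pretest-posttest design there is no control arm to show the same distortion.

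**Working it through.** The plan gives no figure of its own on this point to reproduce. It states no missed-visit rate, no reason-for-absence data and no conversion from the 0-3 levels to the 1-10 scale. The check is a count of calendar days, followed by the score value of one cold.

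**Coverage of the form.** Each form completed on Day v covers Days v-13 to v.
- All four visits attended: 4 x 14 = 56 of 56 days covered.
- One visit missed: 56 - 14 = 42 of 56 (75%). The hole is Days 1-14, 15-28, 29-42 or 43-56, depending on the visit.
- Two visits missed: 28 of 56 (50%).

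**Coverage of Table 2.** Taking 2 months as 60 days (assumed), the window opens on Day v-60: Day -46, -32, -18 and -4 for Days 14, 28, 42 and 56. Asked afresh, it contains every skipped interval that is followed by an attended visit.

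**Worked case.** A cold starts on Day 20 and the Day 28 visit is missed. LOCF copies the Day 14 record to Day 28, so the cold is not in the Day 28 score. The Day 42 form covers Days 29-42. What happens at Day 42 depends on a rule that the protocol does not state:
- (a) Fresh 2-month inquiry: the window opens on Day -18, so the cold is counted at Day 42 and, with a window from Day -4, at Day 56.
- (b) Latest two-week form only: the cold would not count at Day 42 even with full attendance. The absence changes only the Day 28 record.
- (c) Two-week forms added up: the cold is missing at Days 42 and 56 because the visit was missed.

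**Value of one cold.** Assume level k (0 to 3) maps linearly to a sub-score of 10 - 9k/3 = 10 - 3k. One level is then 3 points.
- PQS: 0.25 x 3 = 0.75 points. GQS: 0.20 x 3 = 0.60 points.
- Because the item stops at level 3, the most it can move a participant's PQS is 0.25 x 9 = 2.25 points.
- Over 29 participants, each omitted cold moves the mean PQS by 0.75/29 = 0.026. The number of omitted colds cannot be derived from the documents, so no total follows.

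**The case against.** The strongest reply is that the primary score is not defined on this question. Section 2.5.1.1 and Table 2 make the cold item a practitioner's inquiry over 2 months, and section 2.4 lists a TCM diagnostic work-up at each visit in addition to the form. Appendix III cannot be the whole scoring source: it has no pulse, tongue or voice item, its sweating options differ in wording and order from Table 2, and its Part III and IV items carry no 1-10 rating such as Table 4 needs. This stands. A reader might infer that the skipped interval is never asked about, that the cold disappears from the primary score, and that no analysis could recover it. The documents do not support that, because reading (a) is open and recovers the cold at the next attended visit.

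It does not dispose of the point. Section 2.4 quantifies PQD at screening with Appendix I, the counterpart form; the wind-and-cold answers on both forms closely follow the Table 2 levels; and no follow-up form has a place for a 2-month count. The form is therefore a plausible source, and nothing requires a fresh inquiry to be recorded.

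Two further replies hold in part. First, a cold that causes an absence is symptomatic on the missed day and may run into the next window. For a cold lasting L days, with onset uniform over the L days ending on the missed visit, the share that does so is (L-1)/L: 2/3 = 67% for 3 days and 13/14 = 93% for 14 days. Some participants would then answer yes. If the question is read as asking about onset, the share is 0%. The wording does not settle which reading applies. Second, LOCF can also carry forward a record that already contains a cold, so imputation does not always favour improvement.

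**Conclusion.** The form has a real gap: 14 of 56 treatment days per missed visit, with no catch-up question and a skip that bypasses item 1d. Whether the gap reaches the later scores depends on an unstated scoring rule. It does so under (c). Under (a) and (b) the missed visit affects only its own LOCF record. If no later visit is attended, the cold is lost under any reading.

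For an affected participant, one omitted cold is worth 0.75 PQS or 0.60 GQS points in the direction of better health. This rests on the assumed linear conversion and applies where the true count is three or fewer. A reader might go on to infer a definite bias in the mean PQS. That would need assumed absence rates, an assumed share of absences due to colds, and a rule for adding up the forms; the documents supply none of these, so the mean effect cannot be sized. The point is a cheap improvement to data collection and not evidence that the primary result is biased.

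**What to change.** In Appendix III, Part I:
- Reword question 1 to: *Since your last completed study visit (date ____), did you catch any cold?*, keeping the TCM footnote.
- Record the onset date of each cold.
- Place item 1d before the skip so that everyone answers it.

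In section 2.6, state that the 2-month cold item at each visit is built from these dated episodes, with baseline dates where the window reaches before Day 0. State that this includes a missed visit when a later visit is attended, and that LOCF is used for this item only when no later visit exists. Appendix I records durations and days since last symptoms, but not onset dates, so its two-month question needs the same date field.

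The cost is a wording change, a date field and a short addition to section 2.6. Recall after one missed visit becomes about 4 weeks, still shorter than the 2 months asked at baseline. Colds before a missed Day 56 visit or after withdrawal stay unrecoverable. Version 3 is dated June 2021 and enrolment was planned for March to April 2018. If collection is complete, the form change serves the randomized trial that this study is meant to inform, while section 2.6 can still state how the item was built and flag the intervals that no form covered.
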